4.8.3. Laboratory Data

For each phase of the trial, clinical laboratory data (hematology and biochemistry) at screening, during and at the end of treatment, and the change from baseline to end of treatment will be summarized for the safety analysis set using descriptive statistics. Categorical shift tables will also be presented, showing the numbers of patients with values outside the normal range and values outside of toxicity limits for hematology and biochemistry data.

All hematology, biochemistry and urinalysis laboratory data will be provided in data listings. The values that are below the lower limit or above the upper limit of the reference range and values that are outside of toxicity ranges will be flagged.

GW Toxicity criteria will be summarized for the following lab tests only:

- >3xULN for ALT and AST:
- >2xULN for TBL.

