12.7 Potential Cases of Drug-Induced Liver Injury

All investigational sites are required to submit to the GW PVD the laboratory results for any patient after starting treatment that meets the criteria for the selected laboratory parameters as follows:

- ALT or AST > 3 × ULN with the appearance of fatigue, nausea, vomiting, right upper quadrant pain or tenderness, fever, rash, and/or eosinophilia (> 5%).
- ALT or AST $> 8 \times ULN$.
- ALT or AST $> 5 \times$ ULN for more than 2 weeks.
- ALT or AST $> 3 \times$ ULN and (TBL $> 2 \times$ ULN or INR > 1.5).

These reports must be sent to the GW PVD using the fax number for SAE reporting (see APPENDIX 2) within 24 hours of becoming aware of the results. In addition, please send a copy of the patient's baseline laboratory results with all reports to the GW PVD.

Abnormal values in AST and/or ALT concurrent with abnormal elevations in TBL that meet the criteria outlined above are considered potential cases of drug-induced liver injury and will be considered as protocol-defined criteria for withdrawal and important medical events. The investigator will arrange for the patient to return to the investigational site as soon as possible (within 24 to 48 hours of notice of abnormal results) for repeat assessment of ALT, AST, TBL, alkaline phosphatase and gamma-glutamyl transferase levels, detailed history and physical examination. Patients should be followed in this way until all abnormalities have normalized (in the investigator's opinion) or returned to the baseline state, however, if the above transaminase elevation criteria are confirmed by the first set of follow-up laboratory tests, the patient must be withdrawn from the trial.

Elevations in ALT or AST $> 3 \times \text{ULN}$ or TBL $> 2 \times \text{ULN}$ alone are not considered potential cases of drug-induced liver injury, but will be followed as detailed above, within 72 hours' notice of abnormal results.

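### The SAP's liver toxicity summary counts raised ALT/AST and raised bilirubin separately, and no planned table gives their combination or the other protocol 12.7 criteria

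*SAP*

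**What the plan says.** SAP 4.8.3 plans descriptive statistics for hematology and biochemistry, and shift tables against the reference range and against toxicity limits. It then narrows the toxicity part: "GW Toxicity criteria will be summarized for the following lab tests only". Two items follow, ">3xULN for ALT and AST" and ">2xULN for TBL", each a threshold on a single test. The matching output in SAP 6.1 is Table 13.2.3, a chemistry shift table on toxicity limits. SAP 4.8.3 also promises listings of all laboratory values, with those outside toxicity ranges flagged.

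Protocol 12.7, on potential drug-induced liver injury, lists four criteria under which sites must send results to the sponsor:

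1. ALT or AST above 3×ULN "with the appearance of fatigue, nausea, vomiting, right upper quadrant pain or tenderness, fever, rash, and/or eosinophilia" (above 5%).
2. ALT or AST above 8×ULN.
3. ALT or AST above 5 times "ULN for more than 2 weeks".
4. ALT or AST above 3×ULN, with TBL above 2×ULN or INR above 1.5.

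It goes on to treat ALT/AST abnormalities that coincide with raised TBL and meet the criteria as potential liver injury. Elevations of ALT or AST above 3×ULN, or of TBL above 2×ULN, "alone are not considered potential cases of drug-induced liver injury, but will be followed as detailed above". Protocol section 10 makes all four criteria grounds for mandatory withdrawal, and SAP 2.3 repeats them.

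**The concern.** The two thresholds chosen for the summary are the two that the protocol says do not, by themselves, point to liver injury. The SAP restates the four criteria in section 2.3 and then plans no summary of them. SAP 6.1 has no table for any of the four, SAP 6.2 has no listing of liver cases, and SAP section 5 does not mention the point.

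Laboratory safety is part of the pilot primary endpoint and of the extension's primary long-term safety endpoint (SAP 2.5). Protocol 8.2 describes the risk of valproate hepatotoxicity in this population as high. A reader of the safety tables will want to know how many infants met the protocol's own liver criteria, including whether the answer is zero. As planned, the tables do not say.

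**Working it through.** There is no stated figure to reproduce, and sample size and error rates play no part. The check compares the two documents and adds one piece of arithmetic on what separate counts can show.

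**Step 1: the criteria against the planned outputs.**

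| Protocol 12.7 criterion | Needs ALT/AST above 3×ULN? | Planned table | Where a reader could find it |
|---|---|---|---|
| 1. Above 3×ULN with symptoms or eosinophilia | Yes | None | Listings 13.2, 11.1 and 13.1, matched by date |
| 2. Above 8×ULN | Yes (8 > 3) | None | Listing 13.2 |
| 3. Above 5×ULN for over 2 weeks | Yes (5 > 3) | None | Listing 13.2, with sample dates |
| 4. Above 3×ULN with TBL above 2×ULN or INR above 1.5 | Yes | None | Listing 13.2 for TBL; INR only if recorded |

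So 0 of 4 have a planned table, and 4 of 4 lie inside the category above 3×ULN.

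**Step 2: what separate counts can show.** Suppose *a* of *n* patients have ALT/AST above 3×ULN and *b* have TBL above 2×ULN. The number with both lies between max(0, *a* + *b* − *n*) and min(*a*, *b*). Take *n* = 9 (SAP 4.1) and, as assumed counts for illustration, *a* = 2 and *b* = 1:

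- lower bound: max(0, 2 + 1 − 9) = max(0, −6) = 0
- upper bound: min(2, 1) = 1

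The joint count could be 0 of 9 (0%) or 1 of 9 (11.1%). The two counts do not separate these, nor do they show whether the elevations fell on the same date. If *a* = 0, the upper bound is 0 and the table alone settles the question.

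**Step 3: what a program would need.**

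- *Unscheduled samples.* Protocol 12.7 calls for repeat testing within 24 to 48 hours of notice. SAP 4.2.10 shows by-visit data by nominal visit, so the summary must say that unscheduled repeats count.
- *Duration.* Scheduled samples from Day 71 onward fall on Days 71, 127, 211, 295 and 379, with gaps of 127 − 71 = 56 days and then 84 days each. Criterion 3 therefore needs a persistence rule, which the SAP lacks. In the pilot phase the post-baseline treatment samples are at Day 4 (+1) and Day 15 (+3), at most 18 − 4 = 14 days apart. A run of more than 14 days cannot be shown on those two samples alone.
- *INR.* Protocol Table 9.2.10-1 names prothrombin time, as an additional parameter taken where possible, and does not name INR. INR appears among the optional repeat tests in protocol section 10 but not among the repeats in 12.7.

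**The case against.** The case for leaving the SAP alone has real force.

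- **The threshold contains every case.** Each criterion requires ALT or AST above 3×ULN. If the count is zero there are no cases, and otherwise at most 9 patients need looking up. This stands, provided the count includes unscheduled samples.
- **The patient-level data are there.** All hematology and biochemistry values are listed and toxicity values flagged. In a single-arm descriptive analysis of 9 infants, raised ALT and TBL in one child can be seen directly. This stands too. However, the flags apply to single values, so criteria 1 and 3 require matching listings by patient and date under a rule that the SAP does not give.
- **Cases may surface elsewhere.** Confirmed cases must be withdrawn, and the withdrawal reason is listed (SAP 4.4). Concurrent ALT/AST and TBL cases are important medical events and may appear among serious events or discontinuations. Those tables are organised by system organ class and preferred term, so the cases would not be identified as meeting a liver criterion.
- **Protocol 13.6.5.3 promises no such table.** It asks for summary statistics and normal-range shift tables. The SAP already goes further by adding toxicity limits.

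A reader might also infer that all four criteria are the protocol's definition of liver injury, so that the SAP has omitted every defined case. The heading of 12.7 invites that reading, but the text does not clearly support it. The list is introduced as criteria for sending results to the sponsor, and the sentence that names potential cases refers to ALT/AST abnormalities concurrent with raised TBL. On that stricter reading the other criteria are reporting and withdrawal triggers. The point survives, because the ALT/AST-with-TBL combination is not tabulated either.

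**Conclusion.** The point holds as a weakness of tabulation. SAP 4.8.3 confines the toxicity summary to two separate counts. No planned table gives the combination that protocol 12.7 treats as potential liver injury, or any of the other 12.7 criteria: 0 of 4. With 9 patients, the undetermined part of the joint count is at most a few infants, and it is zero if no one exceeds 3×ULN.

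Two stronger conclusions are tempting, and the documents support neither. One is that liver cases would be missed or their data lost: the category above 3×ULN contains them all, and the flagged listings allow them to be found by hand. The other is that the SAP departs from the protocol's planned analysis: 13.6.5.3 asks for no liver-criteria table, and the gap is relative to section 10 and 12.7.

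This rests on taking the word restricting the toxicity summary at face value, and on SAP 6.1 and 6.2 being the complete list of outputs. What remains is a cheap and worthwhile improvement to how a primary safety endpoint is reported.

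**What to change.** Add to SAP 4.8.3 and Table 13.2.3, for each phase and using all post-baseline samples including unscheduled repeats, the number of patients with:

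- ALT/AST above 3×ULN and TBL above 2×ULN on the same sample date, or INR above 1.5 where INR was measured, stating how many patients had an INR;
- ALT/AST above 8×ULN.

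Report the other two criteria under written rules:

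- *Above 5×ULN for more than 2 weeks:* consecutive samples, all above 5×ULN, with more than 14 days between first and last. State the phase to which a run that crosses from pilot to extension is assigned.
- *Above 3×ULN with symptoms or eosinophilia:* linked by date to the adverse event and hematology listings, with the date window stated.

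Flag every patient who meets a criterion in Listing 13.2, and print zero counts. These are counting conventions for the report and do not change any withdrawal rule.

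The cost is modest extra programming, mostly for the adverse event and date linkage. No new procedure or sample is needed. INR will often be unavailable because only prothrombin time is a named laboratory parameter, so that branch of the combination may rest on few values.

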4.8.4. Vital Signs and Physical Examinations

Vital signs measurements (systolic and diastolic blood pressure, pulse rate, body temperature, respiratory rate, height, weight, BMI, and head circumference), taken in a supine position at rest for 5 minutes, will be completed alongside the physical examination.

Physical examinations will include length (height), body weight, and head circumference measurements.

Vital signs and physical examination data will be summarized at screening, baseline, and at each time point during the treatment period using descriptive statistics. Changes in the vital signs from baseline to end of treatment will also be summarized.

All vital sign and physical examination measurements will be presented in data listings.

4.8.5. Electrocardiogram

ECG recordings (ventricular rate, PR duration, QRS duration, QT duration, and QTCB) will be performed after 5 minutes in a supine position. A physician must review the ECG immediately (annotated, signed and dated) and any abnormal findings considered to indicate significant medical history or AEs must be recorded appropriately on the CRF. Additional ECG measurements can be taken at any time during the trial, if clinically indicated.

ECG data will be summarized at screening, baseline, and at each time point during the treatment period using descriptive statistics.

All ECG measurements will be presented in a data listing.

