6.2 Exclusion Criteria

The patient may not enter the trial if ANY of the following apply:

- 6.2.1 Patient is currently taking or has taken clobazam or any oral mTOR inhibitor within the 2 weeks prior to the screening visit.
- 6.2.2 Patient has a QT interval, corrected for heart rate with Bazett's formula (QTcB), of > 460 msec on ECG.
 - Note: If the QTcB is above > 460 msec, the investigator should repeat the ECG 3 times and contact the GW medical monitor, prior to screen failure or entry into the pilot/pivotal phase.
- 6.2.3 Patient's caregiver is currently giving or has given recreational or medicinal cannabis, or synthetic cannabinoid-based medications, within the 1 month prior to the screening visit, as determined by investigator interview with patient's caregiver.
- 6.2.4 Patient's caregiver is unwilling to abstain from giving the patient (including the patient's mother abstaining themselves, if breastfeeding) recreational or medicinal cannabis, or synthetic cannabinoid-based medications (other than the study IMP) during the trial, as determined by investigator interview with patient's caregiver.
- 6.2.5 Patient has any known or suspected hypersensitivity to cannabinoids or any of the excipients of the IMP(s), such as sesame oil.
- 6.2.6 Patient has significantly impaired hepatic function at the screening visit, defined as any of the following:
 - i) Serum alanine aminotransferase (ALT) or aspartate aminotransferase $(AST) > 5 \times \text{upper limit of normal (ULN)}$.
 - ii) Serum ALT or AST > $3 \times \text{ULN}$ and (total bilirubin [TBL] > $2 \times \text{ULN}$ or international normalized ratio [INR] > 1.5).
 - iii) Serum ALT or AST $> 3 \times ULN$ with the presence of fatigue, nausea, vomiting, right upper quadrant pain or tenderness, fever, rash, and/or eosinophilia (> 5%).

EudraCT Number: 2015-004904-50

Protocol V3 20Sep16

This criterion can only be confirmed once the laboratory results are available; patients must not be allocated any IMP prior to this. **Note:** If transaminases are elevated, the Investigator may choose to confirm the transaminase elevations by repeat testing during the screening period; results should be discussed with the GW medical monitor prior to screen failure or entry into the pilot or pivotal phase.

- 6.2.7 Patient has received an IMP as part of a clinical trial within a minimum of 5 half-lives prior to the screening visit.

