13 STATISTICAL CONSIDERATIONS

13.1 Sample Size, Power, and Significance Levels

The pilot phase is not powered and comprises 10 patients. Both cohorts in the pilot phase will comprise 5 patients, the first cohort aged between 6 and 24 months and the second cohort aged between 1 and 24 months, who will all receive GWP42003-P.

The pivotal phase will comprise 192 patients, aged 1–24 months, who will be randomized to receive 1 of 2 dose levels of GWP42003-P (High Dose Level or Low Dose Level) or matching placebo on a 1:1:1 basis (64 per treatment group). Patients in the placebo group will be further split into 2 cohorts (32 patients receiving Low Dose Level dosing volumes and 32 patients receiving High Dose Level dosing volumes), but it is assumed that these 2 cohorts can be pooled for the analyses of efficacy.

Assuming a 20% screen failure rate, it is expected that approximately 245 patients will need to be screened to achieve this target (202 patients included in the pilot and pivotal phases in total).

This is based on a 2-sided 5% significance level, based on a Fisher's exact test.

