2.3. Stopping Rules and Unblinding

The patient must be withdrawn from the trial if ANY of the following apply:

- Any issue with eligibility criteria that is considered to potentially compromise the safety of the patient.
- Administrative decision by the investigator, GW, or regulatory authority.
- Protocol deviation that is considered to potentially compromise the safety of the patient.
- Withdrawal of the patient's parent(s)/legal representative consent.
- QTcB of 500 msec or greater on ECG, or a shift from baseline QTcB of 60 msec or greater.
- Lost to follow-up.
- ALT or AST $> 3 \times$ ULN with the appearance of fatigue, nausea, vomiting, right upper quadrant pain or tenderness, fever, rash, and/or eosinophilia (> 5%).
- ALT or AST $> 8 \times ULN$.
- ALT or AST $> 5 \times$ ULN for more than 2 weeks.

ALT or AST $> 3 \times$ ULN and (TBL $> 2 \times$ ULN or INR > 1.5). The patient may also be withdrawn from the trial for ANY of the following:

- Any other issue with eligibility criteria (non-safety related).
- Any requirement to increase the dose of concomitant AED(s) or to add in new AED(s) during the pilot or pivotal phase.
- If a patient is not showing evidence of benefit during the OLE phase (the option of withdrawing from the trial will be discussed with the caregiver at each visit).
- Patient/caregiver non-compliance.
- AE (including clinically significant laboratory result) which, in the opinion of the investigator, would compromise the continued safe participation of the patient in the trial.

There is no blinding necessary for the pilot and OLE phases so unblinding procedures will not apply.

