4. STATISTICAL METHODS

4.1. Sample Size Justification

The pilot phase of the study is not powered and comprises of 9 patients.

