4.2.10. Visit Windows

Any clinical domains that are displayed by visit will be shown by nominal study visit.

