- Table 11.5.2 Treatment-Emergent Adverse Events by System Organ Class and Preferred Term and Sex OLE Phase Safety

GW Research Ltd Study Code: GWEP15100 EudraCT Number: 2015-004904-50 25SEP2019

- Table 11.6.1: Non-Serious Treatment Emergent Adverse Events by System Organ Class and Preferred Term for Subjects and Events Pilot Phase Safety
- Table 11.6.2: Non-Serious Treatment Emergent Adverse Events by System Organ Class and Preferred Term for Subjects and Events OLE Phase Safety
- Table 12.1.1 Serious Treatment-Emergent Adverse Events by System Organ Class and Preferred Term Pilot Phase Safety
- Table 12.1.2 Serious Treatment-Emergent Adverse Events by System Organ Class and Preferred Term OLE Phase Safety
- Table 12.2.1 Treatment Related Serious Treatment-Emergent Adverse Events by System Organ Class and Preferred Term Pilot Phase Safety
- Table 12.2.2 Treatment Related Serious Treatment-Emergent Adverse Events by System Organ Class and Preferred Term OLE Phase Safety
- Table 12.3.1 Treatment-Emergent Adverse Events Leading to Study Drug Discontinuation by System Organ Class and Preferred Term Pilot Phase Safety
- Table 12.3.2 Treatment-Emergent Adverse Events Leading to Study Drug Discontinuation by System Organ Class and Preferred Term OLE Phase Safety
- Table 12.4.1 Treatment Related Treatment-Emergent Adverse Events Leading to Study Drug
- Discontinuation by System Organ Class and Preferred Term Pilot Phase Safety
- Table 12.4.2 Treatment Related Treatment-Emergent Adverse Events Leading to Study Drug Discontinuation by System Organ Class and Preferred Term OLE Phase Safety
- Table 12.5.1 Fatal Treatment-Emergent Adverse Events by System Organ Class and Preferred Term Pilot Phase Safety
- Table 12.5.2 Fatal Treatment-Emergent Adverse Events by System Organ Class and Preferred Term OLE Phase Safety
- Table 13.1.1 Summary of Laboratory Test Results and Change from Baseline by Visit Hematology Pilot and OLE Phase Safety
- Table 13.1.2 Summary of Laboratory Test Results and Change from Baseline by Visit Chemistry Pilot and OLE Phase Safety
- Table 14.1 Summary of Vital Signs Results and Change from Baseline by Visit Pilot and OLE Phase Safety
- Table 14.2 Summary of Physical Examination Results and Change from Baseline by Visit Pilot and OLE Phase Safety
- Table 14.3.2 Summary of ECG Results and Change from Baseline by Visit Pilot and OLE Phase Safety
- Table 13.2.1 Hematology Shift Table Based on Reference Ranges Pilot and OLE Phase Safety

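### The SAP plans no count of infants who met the protocol's QTcB limits, has no rule for unscheduled or paired pre- and post-dose ECGs, and could take a Day 1 post-dose ECG as baseline

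*SAP*

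**What the plan says.** - **Summary method.** SAP Section 4.8.5: "ECG data will be summarized at screening, baseline, and at each time point during the treatment period using descriptive statistics". The parameters are "ventricular rate, PR duration, QRS duration, QT duration, and QTCB". Section 4.2.1 gives mean, median, standard deviation, minimum and maximum for continuous variables.
- **Display.** SAP Section 6.1 plans a single ECG table: "Table 14.3.2 Summary of ECG Results and Change from Baseline by Visit Pilot and OLE Phase Safety". Section 4.2.10 adds: "Any clinical domains that are displayed by visit will be shown by nominal study visit". All ECG values also go into Listing 14.2.
- **Individual limits.** SAP Section 2.3, repeating Protocol Section 10, requires withdrawal for "QTcB of 500 msec or greater on ECG, or a shift from baseline QTcB of 60 msec or greater". Protocol Section 10 makes this conditional on confirmation, after three repeat ECGs. The entry criterion in Protocol Section 6.2 is "Patient has a QT interval, corrected for heart rate with Bazett's formula (QTcB), of > 460 msec on ECG".
- **Timing.** By the footnotes to SAP Table 1, the Visit 2 ECG is taken only 3–5 hours after the first dose, and Visits 3 and 4 each have one ECG before the day's first dose and one 3–5 hours after it. Section 4.8.5 also allows extra ECGs at any time.
- **Baseline.** SAP Section 4.2.9 uses the last value before first dosing. Where timing was not recorded, it presumes that a first-dosing-day assessment preceded the dose.
- **Laboratory comparison.** SAP Section 4.8.3 gives hematology and biochemistry shift tables, ALT, AST and bilirubin toxicity summaries, and flagged listings.
- **Size.** SAP Section 4.1: "The pilot phase of the study is not powered and comprises of 9 patients". Protocol Section 13.1: "The pilot phase is not powered and comprises 10 patients".

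**The concern.** SAP Section 2.5 makes safety, with ECG named, a primary endpoint of the pilot and the primary endpoint of the OLE. The pilot also aims to establish the maximum safe, tolerable dose. The natural question for the ECG data is therefore how many infants reached a QTcB limit at any time. No planned output answers it, although the liver tests that also drive withdrawal get toxicity summaries and flags.

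Three gaps in the rules add to this. A crossing seen only on an unscheduled or repeat ECG may never reach the by-visit table. The 3–5 hour post-dose ECG has no stated row of its own and no planned contrast with the pre-dose reading of the same day. A Day 1 ECG with no recorded time could become the reference for later changes although it was scheduled after dosing.

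**Working it through.** Neither document gives a calculation for the pilot or OLE ECG analysis, so there is no figure to reproduce. I checked what each planned output can show. Inputs are n = 9 (SAP 4.1) or 10 (Protocol 13.1), and the 60 and 500 msec limits (SAP 2.3). Heart rates, spreads and QTc levels below are my assumptions.

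1. **Mean and median.** One infant at +60 msec with the others at 0 moves the mean by 60/9 = 6.7 msec (60/10 = 6.0 with 10 infants). In a simulation with the other eight centred on 0 and an SD of 10–20 msec, the median moved by about 1.5–3.1 msec on average. Neither statistic identifies the crossing.

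2. **Maximum.** In the same example the maximum change is at least 60 msec by construction, so the table shows that someone crossed at that visit. It does not show how many. Maxima of 60 or more at two visits could be one infant twice (1/9 = 11%) or two infants (2/9 = 22%).

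3. **Listing.** Scheduled ECGs per infant are 1 (screening) + 1 (Visit 2) + 2 (Visit 3) + 2 (Visit 4) + 8 (Visits 5–12) + 1 (end of taper) = 15. For 9 infants completing every visit that is 9 × 15 = 135 scheduled ECGs, plus any extra ones. The count can be extracted by hand, but no flags are planned.

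4. **Paired ECGs at Visits 3 and 4.** Suppose one infant changes by 0 pre-dose and +60 msec post-dose, and the other eight do not change. What the table shows depends on a layout the SAP leaves open:
   - separate rows: post-dose mean 60/9 = 6.7, maximum 60;
   - 18 records pooled: mean 60/18 = 3.3, maximum 60;
   - averaged within infant: (0 + 60)/2 = 30, so mean 30/9 = 3.3, maximum 30;
   - pre-dose value only: mean 0, maximum 0.

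   Under the last two, the maximum does not reveal the crossing.

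5. **Baseline.** The screening ECG is the only scheduled pre-dose ECG before first dosing. If an untimed Day 1 ECG replaces it and that reading already carries a change of d msec, a later shift S from screening is displayed as S − d. A shift of exactly 60 msec falls below the limit for any d > 0.

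6. **What a count would say.** With 0 of 9 crossing, the exact one-sided 95% upper limit is 1 − 0.05^(1/9) = 28.3% (two-sided 95% interval: 1 − 0.025^(1/9) = 33.6%). With 10 infants these are 25.9% and 30.8%. The chance of at least one crosser, 1 − (1 − p)^9, is 37%, 61% and 87% for true rates of 5%, 10% and 20%. The count describes; it cannot rule out a common effect.

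7. **Heart rate.** QTcB = QT/RR^(1/2) and QTcF = QT/RR^(1/3), so QTcB = QTcF × (HR/60)^(1/6). Holding QTcF at 360 msec, 120 to 150 bpm takes QTcB from 404 to 419 (+15), 110 to 160 from 398 to 424 (+26), and 100 to 180 from 392 to 432 (+40). At QTcF 400 msec, 120 to 150 bpm gives 449 to 466 (+17), passing 460. A rate-only shift of 60 msec from a QTcB of 400–460 needs the rate to rise by a factor of ((QTcB + 60)/QTcB)^6, which is 2.31 to 2.09.

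**The case against.** The strongest reply is that little is hidden. The maximum is planned, Table 14.3.2 covers change from baseline, and Section 4.8.5 lists every ECG without exempting unscheduled ones. A physician reviews each ECG at once, confirmed crossings require withdrawal, the primary withdrawal reason is listed by subject, and adverse events that end treatment are tabulated. The SAP also delivers what Protocol Section 13.6.5.4 asks for ECG, since categorical tables were promised only for laboratory data.

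Much of this stands. A reader might infer that a QT signal would be averaged out of the report. The documents do not support that, because the maximum and the listing remain. A reader might also infer that pre- and post-dose values will be pooled. Section 4.8.5 speaks of each time point, which can mean separate rows, and Section 4.2.10 does not direct merging. The layout is unspecified, not wrong.

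Nor do the figures support the idea that Bazett's correction would by itself manufacture a withdrawal-level shift. The widest rate change assumed gives 40 msec, short of 60, and Fridericia as the constant reference is itself an assumption. Bazett is the protocol's own metric, and QT and ventricular rate are both reported, so another correction can be derived.

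What the reply does not cover is the per-infant count, the status of unscheduled and repeat ECGs in the summaries, and the untimed Day 1 reading. An unconfirmed crossing need not lead to withdrawal, and the listed primary reason need not name QTcB.

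**Conclusion.** The point holds as a gap in specification and presentation, of minor to moderate weight. The planned outputs would show that a large QTcB value occurred at a scheduled visit, provided that ECG enters the by-visit summary as its own value. They would not show how many of the 9 infants met the 500 or 60 msec limit at any time, whether on unscheduled ECGs, or whether the crossing was confirmed. The paired ECGs have no stated display and no within-visit contrast. The baseline rule fits the ECG schedule badly, but does harm only where a Day 1 ECG time is missing and no other rule overrides it; how often that happens cannot be judged from the documents.

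The sizes in the example (6.7 msec in the mean, a maximum of 30 instead of 60 msec under within-infant averaging) rest on one crossing infant and no change in the others. The 9 versus 10 patient difference does not alter the conclusion. The departure is from good reporting practice and from the SAP's own handling of laboratory data, not from the protocol.

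**What to change.** In SAP Sections 4.8.5 and 6.1, with a matching exception in 4.2.9:

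- **Count table, one per phase.** Number of infants with QTcB of at least 500 msec, and with a shift of at least 60 msec from the screening ECG, at any post-dose ECG including unscheduled and repeat recordings. Show confirmed and unconfirmed crossings separately, so that the count can be read against the withdrawal criterion. Show values above 460 msec as a descriptive category only, since that figure is an entry criterion.
- **Flags.** Mark these values in Listing 14.2, as is done for laboratory values.
- **Paired ECGs.** Give Visits 3 and 4 separate pre-dose and 3–5 hour post-dose rows, with the post-minus-pre change. State whether unscheduled and repeat ECGs enter the by-visit rows.
- **Baseline.** State that the Visit 2 ECG is not eligible as ECG baseline when its time is missing.
- **Optional.** Show QTcF, derived from recorded QT and ventricular rate, beside QTcB as supportive only.

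The withdrawal rule is unchanged. The cost is SAP wording, one short table shell, extra rows and flags, all from data already collected.
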